**Methodology:**

*The study consists of a survey on physical activity prior to contracting COVID-19 among patients hospitalized due to this disease at the USK (Temporary Hospital for COVID patients).*

*Time Frame: 01 Nov 2021- throughout the entire period of hospital activity*

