**Exclusion criteria:**

- pregnancy;*
- inability to complete the questionnaire during hospitalization or up to a week after discharge;*
- history of a significant cardiovascular event in the last 6 months (acute coronary syndrome, stroke, amputation, revascularization of peripheral vessels, pulmonary or peripheral embolism of any etiology) if the patient did not complete the rehabilitation process;*
- symptomatic chronic respiratory disease not responding to therapy before hospitalization for COVID-19 (or no therapy);*
- any dyspnea at rest in the last month before COVID-19;*
- injury to the locomotor system in the last month before contracting COVID-19;*
- hospitalization in the last month before contracting COVID-19.*

*In order to describe the group and analyze the survey results, information from the patient's interview, physical examination, and the results of basic and additional tests contained in the patient's hospital documentation during the stay due to COVID-19 will be used.*

*The International Physical Activity Questionnaire (IPAQ) short form will be used to determine the level of physical activity.*

*After consenting to participate in the study, the patient will be asked to answer 7 survey questions. If the patient's condition prevents participation in the survey, the patient will be allowed to participate on a different day, including within 7 days from discharge, or indicate a relative who can fill out the survey for the patient.*

*Each patient will be given an identification number, and the list of participants will be prepared.*

*Data from medical records will be prospectively collected for Primary Outcome Measures: death due to COVID-19, recovery – patients discharged home, transfer to intensive care unit (ICU), and Secondary Outcome Measures: hospitalization length before transfer to intensive care unit, laboratory tests. Additional data – lab results, comorbidities, pharmacotherapy history, and complications related to hospitalization – will be collected if available.*

*Then, they will be combined with the IPAQ results (the surveys will be analyzed anonymously, and paper version of IPAQs will be archived in Uniwersyteckie Centrum Rehabilitacji, [name]) in one document (Excel, based on the patient number).*

*Data ready for statistical analysis will be sent to a statistician and analyzed according to the Statistical Analysis Plan (SAP).*

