*There is no information in the literature on the impact of daily physical activity (obtained directly from patient questionnaires) on the course of COVID-19. Learning what relationships (if any) exist between them can help plan the prevention of this infectious disease and assess the strength of behavioral actions with their impact on the prognosis.*

Additional documents (underline as appropriate)

- a copy of the Rector's decision to grant funding as part of the statutory activities of the University
- information for persons participating in a medical experiment containing detailed data on the purposes and principles of conducting the research, expected therapeutic and other benefits for these persons, and the risk associated with participation;
- a written commitment signed by the researcher to obtain informed consent from all test subjects or their legal representatives;
- a template of the patient's or their legal representative's consent form, which contains statements regarding:
  - voluntary consent to participate in the medical experiment after reading the information,
  - confirmation of the right to ask the researcher questions and receive answers to these questions,
  - information about the possibility of withdrawing from participation in the study at any stage;
- information on the method of collecting and processing personal data for the person participating in a medical experiment;
- research insurance information;
- consent of the person participating in a medical experiment or their legal representative to the processing of data relevant to participation.
- consent of the Head of the USK Temporary COVID Hospital/s (available at the Bioethics Committee office)
- IPAQ – polish version-  
[https://www.academia.edu/19229070/Mi%C4%99dzynarodowy\\_Kwestionariusz\\_Aktywno%C5%9Bci\\_Fizycznej\\_IPAQ\\_wersja\\_polska](https://www.academia.edu/19229070/Mi%C4%99dzynarodowy_Kwestionariusz_Aktywno%C5%9Bci_Fizycznej_IPAQ_wersja_polska)

Head  
of the organizational unit  
implementing the project

.....  
Signature, stamp

Applicant

.....  
Signature, stamp

Wrocław, .....

---

References:

Brodin P. Immune determinants of COVID-19 disease presentation and severity. *Nat Med.* 2021 Jan;27(1):28-33. doi: 10.1038/s41591-020-01202-8. Epub 2021 Jan 13. PubMed ID: 33442016

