## Statistical Analysis Plan

Sample size calculation for confidence interval: 95%; fraction size: 0.5; max error: 5%: 384 participants.

The variables subjected to statistical analysis will be on nominal scales – including dichotomous ones – and ratio scales:

- variables expected in the ratio scales: raw MET, hospitalization length, age, BMI, and concentration levels of all biochemical factors studied;

- variables expected in dichotomous scales: sex, oxygen therapy need (Yes/No), information about patient death or transfer, information about complications, variables describing the study group in terms of history and comorbidities, and medication groups.

The variables in the interval scales are nicotine addiction and IPAQ level (the latter will be treated as a directional, three-item interval variable).

Statistical analysis will begin by verifying the accuracy of the data contained in the compiled database. For this purpose, descriptive statistics with histograms will be determined for ratio variables and tables of sample sizes for nominal variables. Then all extreme outliers and dubious results will be verified again with the source materials. Gaps found in the database will not be replaced with any other values.

In the case of variables on ratio scales, their normality of distribution will be assessed. The Shapiro-Wilk W test will determine the normality of distribution. Characterization of this group of variables will be based on the statistical significance of the W-test. The following descriptive statistics will be defined for variables with a normal distribution: size, mean value, standard deviation, and 95% confidence interval for the mean value. While size, median, and range will be determined for variables that are not normally distributed.

The Shapiro-Wilk W test with a significance level of  $\alpha=0.05$  will be used to evaluate the normality of distributions.

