Principal component analysis (PCA) will assess global relationships between the key variables, regardless of scale. PCA additionally allows the identification of non-obvious and difficult-to-predict correlations between analyzed variables on different measurement scales. The developed PCA model will be estimated using the NIPALS algorithm. The convergence criterion will be set at 0.00001, and the maximum number of iterations will be 100. The number of components will be determined by establishing the maximum predictive ability of  $Q^2$  using V-fold cross-validation, adopting  $V_{max}=7$ . The optimal PCA model will be reduced to principal components, and the results will be presented in a graph, including the contribution of each component to the overall percentage of explained variance and information on their statistical significance.

Pearson correlation coefficient matrices and Spearman's rank correlation coefficients will be calculated to determine correlations between variables of ratio scales.

Their statistical significance will be determined with a t-test adopting a significance level of  $\alpha=0.05$ .

The basis for assessing the correlation of nominal variables will be the significance of Pearson's chi-squared test. In the case of dichotomous variables, for which it will be possible to construct bivariate (2x2) tables, an additional odds ratio (OR) will be determined, along with a 95% confidence interval (OR $\pm$ 95%CI).

A nonparametric Cox proportional hazards model will be used to evaluate the effect of the IPAQ value on survival probability.

The data analysis will also involve testing the statistical significance of differences between mean values: the parametric Student's t-test for independent samples and parametric analysis

of variance (ANOVA) with the post-hoc least significant difference (LSD) test for variables that meet the normality of distribution and homogeneity of variance assumptions, or the nonparametric Mann-Whitney U-test and nonparametric Kruskal-Wallis ANOVA for variables not meeting these assumptions. In addition, Levene's test and the Brown-Forsythe test will assess the homogeneity of variance.

A significance level of  $\alpha=0.05$  will be assumed for all statistical analyses.

Statistical analysis will be performed using StatSoft's Statistica 13.3 PL.

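### The Cox model is meant to show an effect on survival probability, but if discharge home is censored, as is likely, its hazard ratio is cause-specific and does not give that effect

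*Combined protocol and SAP*

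**What the plan says.** The only time-to-event analysis is one sentence in the Statistical Analysis Plan: "A nonparametric Cox proportional hazards model will be used to evaluate the effect of the IPAQ value on survival probability". The event, time origin, per-patient horizon and handling of discharge and ICU transfer are not given there or elsewhere in the available text.

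The rest has to be pieced together:

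- **Outcomes.** The Study Plan (text after the exclusion criteria) takes these primary outcomes from medical records: "death due to COVID-19, recovery – patients discharged home, transfer to intensive care unit (ICU").
- **Contact after discharge.** The only one described is for the questionnaire, which a patient too ill to answer may complete later: "participate on a different day, including within 7 days from discharge".
- **Time frame.** Under Methodology it starts on 01 Nov 2021 and runs "throughout the entire period of hospital activity". That is a calendar window, not a follow-up time per patient.
- **Variables.** The Statistical Analysis Plan lists "information about patient death or transfer" among the dichotomous variables. Length of stay appears under "variables expected in the ratio scales: raw MET, hospitalization length, age, BMI, and concentration levels of all biochemical factors studied", not divided by how the stay ended.
- **Other analyses.** The Statistical Analysis Plan also has chi-squared tests for nominal variables, odds ratios with 95% intervals for 2x2 tables, correlations of ratio variables, and group comparisons.

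**The concern.** A patient who goes home can no longer die in hospital, so discharge alive competes with in-hospital death. The probability of dying in hospital depends on both the death rate and the discharge rate. A Cox model that censors discharge estimates the ratio of death rates among patients still in hospital and leaves the discharge rate out. Converting such a model to a survival probability treats discharged patients as if they kept the death rate of those still on the ward.

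The Study Plan says of its results that they "can help plan the prevention of this infectious disease and assess the strength of behavioral actions with their impact on the prognosis". If activity is related to speed of recovery, the hazard ratio could understate or miss a difference in in-hospital mortality, and in some configurations point the other way. Because the coding of discharge is open, the choice could also be made after the data are seen.

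**Working it through.** **The plan's own figure.** The sample size is for one proportion: n = 1.96² × 0.5 × 0.5 / 0.05² ≈ 384, which reproduces. It involves no hazard ratio or event count and serves here only to scale the result.

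**Inputs.** The documents give no death or discharge rates, so all rates below are assumptions. They show direction and possible size, not the size in this study. Hazards are constant: death d = 0.01/day, discharge r = 0.06/day. In the more active group the death hazard is h·d and the discharge hazard k·r.

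**Step 1: survival probability within one group.**

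- Discharge censored: 1 − exp(−0.01 × 30) = 25.9% dead by day 30.
- True in-hospital risk: d/(d+r) × [1 − exp(−(d+r) × 30)] = 0.1429 × [1 − exp(−2.1)] = 12.5%.

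This gap exists even if IPAQ is unrelated to discharge. With other assumptions (death 0.015/day, discharge 0.085/day, day 28) the figures are 34.3% and 14.1%.

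**Step 2: hazard ratio against risk, between groups.** Final in-hospital death is p = d/(d+r). The odds of death are d/r, so OR = h/k, while the discharge-censored Cox hazard ratio is h. They agree only if k = 1.

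For equal death hazards (h = 1, hazard ratio 1.00), with 192 patients per group:

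| k | In-hospital death, less vs more active | OR = 1/k | Expected deaths | SE(log OR) | ln(k)/SE |
|---|---|---|---|---|---|
| 1.0 | 14.3% vs 14.3% | 1.00 | 27.4 + 27.4 | 0.292 | 0 |
| 1.1 | 14.3% vs 13.2% | 0.91 | 27.4 + 25.3 | 0.297 | 0.32 |
| 1.2 | 14.3% vs 12.2% | 0.83 | 27.4 + 23.4 | 0.302 | 0.60 |
| 1.5 | 14.3% vs 10.0% | 0.67 | 27.4 + 19.2 | 0.317 | 1.28 |

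Example, k = 1.5: p = 0.01/(0.01 + 0.09) = 10.0%; SE = √(1/27.4 + 1/164.6 + 1/19.2 + 1/172.8) = 0.317; ln 1.5 = 0.405; 0.405/0.317 = 1.28.

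**Step 3: other combinations.**

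- h = 0.80, k = 1.0: 0.008/(0.008 + 0.06) = 11.8%, OR 0.80, equal to the hazard ratio.
- h = 0.80, k = 1.5: 0.008/(0.008 + 0.09) = 8.2%, OR 0.53.
- h = 1.25, k = 1.5: 0.0125/(0.0125 + 0.09) = 12.2%, OR 0.83. The hazard ratio points to harm while the risk is lower than 14.3%.

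**Step 4: the coding choice changes the answer.** Take h = 1, k = 1.5. If discharged patients instead stay at risk to day 30, with no later deaths assumed, the hazard ratio solves ∫₀³⁰ [f₁ − (f₀+f₁)·HR·S₁/(S₀ + HR·S₁)] dt = 0. In each group f = d·exp(−(d+r)t) and S = 1 − d/(d+r)·[1 − exp(−(d+r)t)], with that group's own rates. The solution is 0.75, against 1.00 with discharge censored. Simulated Cox fits under the other assumptions (day 28, k = 1.5) gave 0.72 and 0.99.

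**The case against.** **The cause-specific hazard ratio is legitimate.** This stands. A reader might infer that the Cox model is invalid. It is not: it validly describes the association of IPAQ with the rate of death among patients still in hospital. Only its reading as an effect on survival probability fails.

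**Censoring at discharge is not in the text.** This also stands. A reader might infer that the plan fixes in-hospital-only follow-up. The phrase "contained in the patient's hospital documentation during the stay due to COVID-19 will be used" looks like support, but that sentence concerns data for describing the group and analysing the survey. The outcome sentence refers to medical records without limiting them to the stay. In-hospital follow-up is the likely reading because no later vital-status check is described, but the available text is incomplete.

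**Other planned tests could show the difference.** Largely fair. A reader might infer that nothing in the plan would reveal it. In fact the chi-squared and odds-ratio analyses may compare death across IPAQ levels without any censoring rule, although IPAQ level is called an interval variable, so this is not certain. Length-of-stay comparisons may also pick it up. At k = 1.5 mean stays are 1/0.07 = 14.3 and 1/0.10 = 10.0 days; with exponential stays the SE is √(14.3²/192 + 10.0²/192) ≈ 1.26 days, so z is about 3.4. But these analyses are not tied to the survival conclusion, and they mix stays ended by death with stays ended by recovery.

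**The size depends on k.** Correct. At k = 1.1 to 1.2 the gap is well inside sampling error. The sign reversal needs activity to raise the death hazard while speeding discharge, and nothing in the documents suggests that.

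**Death or transfer as a composite.** This is a weak reading of the variable list, since the outcomes name the two separately. It shows only that the event should be stated.

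**Conclusion.** The concern holds in a limited form. The stated target, survival probability, is not what a discharge-censored Cox hazard ratio estimates, and the plan leaves open the choices that decide what the model does estimate. Writing down the event, origin and horizon would not be enough on its own, because the mismatch with the target would remain.

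Two sizes matter, both under assumed constant hazards. A survival curve that censors discharge roughly doubles in-hospital death at day 30 (25.9% against 12.5%), whether or not IPAQ affects discharge. The contrast between IPAQ groups is distorted only if discharge rates differ: by about 0.3 to 0.6 standard errors at ratios of 1.1 to 1.2, and 1.3 at 1.5. That is at most comparable to sampling error at this sample size, but it is systematic and more patients would not remove it. A link between activity and recovery lies within the study's own question, since discharge home is a primary outcome.

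The conclusion rests on in-hospital follow-up with discharge censored. If vital status is obtained to a fixed day for everyone, the problem largely goes away and the plan only needs to say so. The point should be fixed, but it does not undermine the study.

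**What to change.** In the Cox paragraph of the Statistical Analysis Plan:

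1. Define the model: time from admission, a stated horizon, and the event (COVID-19 death or any in-hospital death). If only COVID-19 deaths count, say how other deaths are treated.
2. Say how discharge home is handled and label the resulting hazard ratio cause-specific.
3. Say how ICU transfer is treated and whether deaths after transfer are captured.
4. Report cumulative incidence of death and of discharge alive by IPAQ level, as competing events.
5. Base the survival-probability statement on these curves, or on a logistic regression of final in-hospital status on IPAQ level, not on the Cox hazard ratio alone.
6. Where length of stay is related to MET or IPAQ, analyse it as time to discharge alive with death as a competing event.

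The cost is a few sentences and modest extra analysis, using admission, transfer, discharge and death dates expected in hospital records. Logistic regression of final status is the simplest route. Cumulative incidence may need software other than the named package, and deaths after transfer may need a check of ICU records.

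### Variables that are normal within groups but have unequal variances are sent to rank tests, which do not hold 5% for equal means when group sizes also differ

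*Combined protocol and SAP*

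**What the plan says.** All references are to the Statistical Analysis Plan.

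- **Aim of the comparisons:** "The data analysis will also involve testing the statistical significance of differences between mean values".
- **Route to Student's t-test or ANOVA (with LSD post hoc):** only "for variables that meet the normality of distribution and homogeneity of variance assumptions". Both conditions are required.
- **Every other variable:** "or the nonparametric Mann-Whitney U-test and nonparametric Kruskal-Wallis ANOVA for variables not meeting these assumptions".
- **Variance check:** Levene's test is used, and "the Brown-Forsythe test will assess the homogeneity of variance". Both are named only as checks. No Welch-type test appears anywhere.
- **Level:** 0.05, which "will be assumed for all statistical analyses".
- **Summaries:** these depend on Shapiro-Wilk alone. The plan gives "variables with a normal distribution: size, mean value, standard deviation, and 95% confidence interval for the mean value"; other variables get size, median and range.
- **Groupings:** dichotomous variables include oxygen need, complications and "information about patient death or transfer". For three or more groups: "The variables in the interval scales are nicotine addiction and IPAQ level", the latter with three categories.

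**The concern.** A variable can be normal in each group and still differ in spread between groups. For it, a test of means that allows unequal variances is available and appropriate, but the plan sends it to Mann-Whitney or Kruskal-Wallis. The null variance used by those tests assumes identical distributions in the groups. When both spread and size differ, that variance is wrong even if the centres are equal.

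The groups here are formed by outcome, comorbidity or activity level, not by allocation, so nothing makes them equal in size. If the smaller group is the more variable one, a p-value below 0.05 can reflect spread rather than location. If the larger group is the more variable one, real differences are missed more often. Where the summary shows means with their confidence intervals, a reader would take the p-value beside them as a test of those means.

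**Working it through.** **1. Inputs.** From the plan: the routing rule, Shapiro-Wilk at 0.05, Levene and Brown-Forsythe, the 0.05 level (sidedness not stated; two-sided assumed) and 384 participants. Assumed, because the documents do not give them: group sizes, SD ratios and normality within groups.

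**2. The plan's own figure.** n = z² × p(1 − p) / e² = 1.96² × 0.25 / 0.05² = 384.16, which reproduces 384. This is a precision calculation for one proportion. It is used below only as the total N.

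**3. Mann-Whitney in closed form.** Let group 1 (size n1) have SD r and group 2 (size n2) have SD 1, with equal means, and let s = r² + 1. In large samples:

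- true variance V = [0.25 + (n2 − 1)·c1 + (n1 − 1)·c2] / (n1·n2), with c1 = arcsin(r²/s)/2π and c2 = arcsin(1/s)/2π
- variance assumed by the test V0 = (n1 + n2 + 1) / (12·n1·n2)
- rejection rate = 2[1 − Φ(1.96·√(V0/V))]

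For 77 and 307 with r = 2: c1 = arcsin(0.8)/2π = 0.1476 and c2 = arcsin(0.2)/2π = 0.0320. V = (0.25 + 306 × 0.1476 + 76 × 0.0320)/23,639 = 0.00202. V0 = 385/283,668 = 0.00136. √(V0/V) = 0.819, and 1.96 × 0.819 = 1.605, so the rate is 10.9% (simulated 10.9%). With the sizes exchanged (307 at SD 2, 77 at SD 1) the formula gives 1.6% (simulated 1.7%). With r = 1, c1 = c2 = 1/12, so V = V0 and the rate is 5% for any sizes.

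**4. The whole planned rule.** Simulated: Shapiro-Wilk, then the variance checks, then Student's t or Mann-Whitney. Normal data, equal means, 10,000 datasets per row, Monte Carlo SE about 0.1 to 0.3 points.

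| Group sizes | SD ratio, same order | Planned rule | Welch |
|---|---|---|---|
| 38 / 346 | 2:1 | 12.2% | 4.7% |
| 38 / 346 | 1.5:1 | 9.3% | 4.6% |
| 77 / 307 | 2:1 | 10.9% | 5.1% |
| 77 / 307 | 1.5:1 | 8.4% | 4.8% |
| 134 / 250 | 1.5:1 | 6.9% | 5.1% |
| 77 / 307 | 1:2 | 1.5% | 5.1% |
| 192 / 192 | 2:1 | 5.8% | 5.0% |
| 58 / 326 | 1:1 | 5.2% | 5.1% |

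Repeat simulations of the same rule gave 12.1% to 12.8% for the first row, 8.3% to 8.4% for the fourth and 1.5% to 1.9% for the sixth. Testing normality within groups or on the whole variable changes these rates by at most 0.1 point.

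**5. Three groups** (20,000 datasets each), planned rule against Welch's ANOVA. Sizes 192/134/58 with SDs 1/1.2/2: 8.8% against 5.1%. Sizes 230/115/39, same SDs: 9.8% against 5.1%. Sizes 58/134/192, same SDs: 3.4% against 5.1%. Equal groups of 128: 5.5% against 4.9%. Equal SDs: 5.0% against 4.9%.

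**6. Lost power when the larger group is more variable.** At 77/307, SD 1:2, with a true difference giving Welch about 80%, the planned rule has 61.3%. A rule using Welch for variables judged normal has 79.6%. In that simulation, variables failing normality went to Brunner-Munzel.

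**7. Mild ratio, 1.2:1.** The planned rule rejects about 7%. At 38/346, 5.3 of 7.1 points (75%) come from Student's t, because the variance check missed the difference. At 77/307 it is 3.8 of 7.4 points (51%).

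**8. Summary beside p-value.** If Shapiro-Wilk is applied to the whole variable, two normal groups with clearly different SDs form a mixture that usually fails. At 2:1 it passed in 25% (38/346), 9% (77/307) and 7% (134/250) of datasets. At 1.5:1 it passed in 68% to 82%, and at 77/307 with 1:2 in 75%.

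**The case against.** **The reference to means may be a loose heading.** It introduces a list that includes rank tests. This does not rescue the level. With normal data and equal means, the medians are also equal and neither group tends to larger values, so the rate is off for any of these location hypotheses.

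**The rank test is the lesser evil.** This stands. At 77/307, 2:1, Student's t rejects 18.2% against 10.9% for Mann-Whitney. The fallback is better than ignoring unequal variances, but it is not a 5% test.

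**Reach is narrow and the inputs are assumed.** This stands. At 384 patients Shapiro-Wilk rejects a gamma variable of skewness 0.5 in 95% of samples, so many laboratory, MET and length-of-stay values will probably leave the normal route. The size of the error depends on assumed splits and SDs; its direction does not.

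**Stronger readings that the documents do not support:**

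- A reader might infer that a mean and its confidence interval will always sit beside a rank-test p-value. The plan does not say whether normality is judged on the whole variable or within groups. On the whole-variable reading, step 8 shows that the mismatch is uncommon when the smaller group has about twice the SD, and common at milder ratios.
- A reader might take the excess at 1.2:1 as evidence against the rank tests. Step 7 shows that half to three quarters of it comes from Student's t after a weak pre-test. That is a separate reason to drop the pre-test.
- A reader might conclude that rank tests are wrong for the skewed variables too. The point does not reach those variables beyond how the result is described.

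**Conclusion.** The point holds for ratio variables that are normal within groups when both SDs and group sizes differ. For these, the plan has no test that holds its own 5% level for equal means. Under the assumed settings the rate is about 7% to 12% when the smaller group is 1.5 to 2 times as variable, and about 2% at 77/307 when the larger group is twice as variable. Welch stays near 5%. With equal groups or equal SDs the departure is small (about 6% at 192/192, 2:1).

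The documents do not show how many variables qualify; age or BMI might. They also do not support the inference that the study's main conclusions are unreliable. These are unadjusted supporting comparisons, beside a Cox model for IPAQ and survival. Low priority: worth changing because the change is easy.

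**What to change.** In the Statistical Analysis Plan, replace the sentence on group comparisons with:

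*For variables that pass Shapiro-Wilk (0.05) in every group, means will be compared by Welch's t-test (two groups) or Welch's ANOVA with pairwise Welch comparisons (three or more groups), without a preliminary test of variances. Other variables will be compared by Mann-Whitney or Kruskal-Wallis, reported as comparisons of distributions, not of means. Levene and Brown-Forsythe results will be descriptive only.*

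The summary statistics should follow the same within-group normality decision. Brunner-Munzel is an option for the second branch but is not needed for this point. Multiplicity among pairwise comparisons is a separate matter.

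**Effect.** With normal data the two-group rule gave 4.6% to 6.0%. The three-group rule gave 4.9% to 6.1% over six settings, where the planned rule gave 3.4% to 9.8%. The remaining three-group excess comes from Kruskal-Wallis after chance Shapiro-Wilk failures (1 − 0.95³ = 14% of datasets).

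**Limit.** The change does not make a rank test a test of means. With lognormal data (coefficients of variation 1 and 0.5, groups 38/346, equal means) the planned rule rejects 50%, and the amended rule sends such data to the same test. Hence the reporting wording.

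**Cost.** One sentence, and a check that the named software offers the procedures. When variances are in fact equal, power goes from 80.0% to 78.9% (38/346), 80.2% to 80.0% (77/307) and 80.1% to 80.1% (192/192). These figures come from the variant with Brunner-Munzel in the second branch; power with Mann-Whitney there was not simulated separately.
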